#### **4.3.3.2 Consolidation therapy for IR patients with an HLA identical sibling:**

Patients in CR/ CRi after induction therapy should receive a consolidation therapy based on allogeneic transplantation from an HLA identical sibling. The patients will be censored for outcome analysis at the beginning of conditioning chemotherapy for transplantation and will not receive any further treatment with Sorafenib. If there is no family donor availability, patients proceed with treatment as described under 4.3.3.1.

#### **4.3.3.3 Consolidation therapy for HR patients:**

All patients in CR/ CRi after induction therapy should receive a consolidation therapy based on allogeneic stem cell transplantation. This may involve transplantation procedures from either an HLA identical sibling or an unrelated HLA-matched donor. The patients will be censored for outcome analysis at the beginning of conditioning chemotherapy for transplantation and will not receive any further treatment with Sorafenib. If there is no donor availability, patients proceed with treatment as described under 4.3.3.1.

#### **4.3.4 Maintenance therapy**

Maintenance therapy will be given to patients who received 3 courses of consolidation therapy with high dose AraC and Sorafenib/ Placebo.

#### **4.3.4.1 Arm P**

Patients will not receive any maintenance therapy, but Placebo (2 tablets) twice daily, starting on day 8 of the last consolidation cycle. Maintenance therapy will be administered continuously until one year after start of maintenance therapy.

#### **4.3.4.2 Arm V**

All patients in CR after consolidation therapy will receive a maintenance therapy with Sorafenib 400 mg twice daily (2 tablets twice a day = 800 mg/day). Maintenance therapy will start on day 8 of the last consolidation cycle. Maintenance therapy will be administered continuously until one year after start of maintenance therapy.

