#### **4.1.6 Drug accountability**

Packaging, labeling and distribution will be performed by the Dresden pharmacy (Klinikapotheke des Universitätsklinikums Dresden) on behalf of the sponsor.

The drug will be distributed to the center pharmacies or to the responsible investigator in the center in plastic bottles containing an approximately 1 month drug supply (140 tablets of 200 mg Sorafenib each or Placebo), labeled according to the scheme described above (see chapter 3.3.1). The centers will be supplied with 18 bottles of medication for the initial treatment of 6 patients (3 x 3 bottles for treatment arm A and 3 x 3 bottles for treatment arm B) immediately after initiation. Three bottles contain 420 tablets (140 tablets per bottle) and are sufficient for a minimum treatment with study medication of 105 days, i.e. covering at least the first two courses of induction therapy and the first and second course of consolidation depending on daily dose and time interval between consolidations (see chapter 4.3).

The delivery of the initial three bottles per patient will be part of the starter kit and new starter kits will be organized by the Studienzentrale SAL when needed. Each local center is responsible for ordering more supply for each patient after use of the first three bottles. Each center will have to reorder when the patient starts to use the first tablets from the last remaining bottle. The reorder has to be done via the Studienzentrale SAL. Here the order will be documented and the pharmacy will be informed immediately.

With the first re-order (Erste Nachbestellung), the pharmacy will send 5 bottles sufficient for a minimum of 175 days, i.e. covering at least 5.5 months of maintenance therapy (maintenance therapy starts at day 8 of the third course of consolidation).

With the second re-order (Zweite Nachbestellung), the pharmacy will send 6 bottles sufficient for a minimum of 210 days, i.e. covering the remaining 6.5 months of maintenance therapy.

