### 4.3.3 Consolidation therapy

#### 4.3.3.1 Consolidation therapy for LR patients as defined by cytogenetics and for IR patients without an HLA-identical sibling

All patients in CR/ CRi after induction therapy should receive three courses of HD-AraC consolidation therapy not earlier than one week after attaining CR/ CRi. If, in the opinion of the treating physician, the patient's condition does not allow for consolidation therapy, consolidation therapy can be postponed for up to 4 weeks after a CR/ CRi is reached. However, if the patient is not attaining CR/ CRi 5 weeks after the beginning of the second induction therapy course he/she should be classified as treatment failure (definition of event and EFS see chapter 7) and study treatment should be terminated .

Criteria for the beginning of each consolidation course: platelets > 70.000/μl and neutrophils > 1.000/μl.

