## 5.2 Schedule of evaluations

	Within 10 days prior to the first course of induction therapy	Between day 1 and day 22 of first course of induction chemotherapy	Early response evaluation (d 16)	Before the second course of induction therapy	From day 1 of second course of induction chemotherapy until start of consolidation therapy	Remission control – latest 35 days after the beginning of second induction	Before each course of consolidation therapy	From the beginning of first course of consolidation until the end of third course of consolidation = beginning of maintenance therapy	Postremission control latest day 35 after begin of each course of consolidation therapy
Informed consent	X								
Medical history	X								
Performance status and physical examination	X			X			X		
Vital Signs (blood pressure and pulse) a	X	Daily measurement of blood pressure		X	weekly		X	weekly	
Body weight and height	X			X			X		
CBC (with differential and platelets) a	X	3 times / week		X	weekly	X	X	weekly	X
Chemistry and coagulation a	X	3 times / week		X	weekly		X	weekly	

	Within 10 days prior to the first course of induction therapy	Between day 1 and day 22 of first course of induction chemotherapy	Early response evaluation (d 16)	Before the second course of induction therapy	From day 1 of second course of induction chemotherapy until start of consolidation therapy	Remission control – latest 35 days after the beginning of second induction	Before each course of consolidation therapy	From the beginning of first course of consolidation until the end of third course of consolidation = beginning of maintenance therapy	Postremission control latest day 35 after begin of each course of consolidation therapy
ECG and echocardiography a	X			X			X		
Pregnancy test e	X								
Bone marrow aspirate	X		X			X			X b
Bone marrow biopsy	X								
Bone marrow and blood samples for exploratory research	X		X			X			X b

Table 14: Schedule of evaluation I (prior to and during induction/ consolidation therapy)

	Start of maintenance therapy	During maintenance therapy	End of maintenance therapy	Follow-up 3, 6, 9, 12, 15 and 18 months after end of maintenance therapy	Relapse (during study treatment or follow-up)
Performance status and physical examination	X	monthly	X	X	
Vital Signs (blood pressure and pulse) a	X	monthly	X		

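### The maintenance entry rule contradicts itself: one section asks only for three consolidation courses, another (Sorafenib arm only) asks for CR after consolidation, a status not yet known on the stated start day

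*Protocol*

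**What the plan says.** Who enters maintenance is stated in three places in section 4.3.4:

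- The opening paragraph: "Maintenance therapy will be given to patients who received 3 courses of consolidation therapy", with high-dose AraC and study drug. No remission status is required.
- Section 4.3.4.1 (Arm P): "Patients will not receive any maintenance therapy, but Placebo (2 tablets) twice daily, starting on day 8 of the last consolidation cycle". Again no remission status is required.
- Section 4.3.4.2 (Arm V): "All patients in CR after consolidation therapy will receive a maintenance therapy with Sorafenib 400 mg twice daily". Here CR is required, and CRi is not mentioned.

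Upstream, section 4.3.3.1 opens consolidation to both remission categories: patients "should receive three courses of HD-AraC consolidation therapy not earlier than one week after attaining CR/ CR i".

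On timing, section 4.3.4.2 says "Maintenance therapy will start on day 8 of the last consolidation cycle", section 4.3.4.1 names the same day, and section 4.1.6 agrees: "maintenance therapy starts at day 8 of the third course of consolidation". A column header of Table 14 (section 5.2) instead treats the end of the third course as the beginning of maintenance. The remission check after each course is the "Postremission control latest day 35 after begin of each course of consolidation therapy".

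**The concern.** An entry rule has to give the same answer at every site and has to be answerable on the day it is used. This one does neither.

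A patient who has completed three courses but is in CRi enters maintenance under 4.3.4 and 4.3.4.1 and is not covered by 4.3.4.2. Investigators do not know the arm, so they cannot apply a condition that exists for Arm V alone. Each site must either apply the CR condition to everyone or ignore it.

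The condition also refers to a status after consolidation, while the start is fixed inside the last course, before that course's remission control. At stake are up to one year of study drug for patients not in CR, the start of the one-year clock, the follow-up visits counted from its end, and membership of the per-protocol set, which section 7.2 restricts to patients treated in full adherence to the protocol.

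**Working it through.** **1. Can the CR condition be answered on day 8?**

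- Last AraC day of a course: day 5 (Tables 12 and 13). Day 8 is 8 − 5 = 3 days later.
- CR (section 7.2.1) needs platelets above 100,000/μl, granulocytes above 1,000/μl, marrow blasts below 5% and a stable hemoglobin without transfusion, among other items.
- Remission control for the course: day 35 at the latest. Gap from the stated start: up to 35 − 8 = 27 days.
- Marrow: footnote b to the schedule limits the marrow at that control to patients in a morphologic leukemia-free state or with suspected relapse. Table 15 plans no marrow at the start of maintenance; footnote c puts the first one a month later.

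The schedule therefore does not supply a post-consolidation remission status by day 8.

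**2. Can a CRi patient reach this point?**

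Yes. Section 4.3.3.1 admits CRi patients, and a course may begin with platelets above 70,000/μl and neutrophils above 1,000/μl. A patient with platelets between 70,000 and 100,000/μl, neutrophils above 1,000/μl and a clear marrow meets that criterion and is in CRi, not CR. The CRi gap in 4.3.4.2 concerns patients the protocol itself takes through consolidation.

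**3. Does the start day change exposure?**

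Tables 12 and 13 give two tablets twice daily from day 8 of every consolidation course. Maintenance uses the same tablets, number and frequency. After the third course there is no next course to stop for, so dosing runs on. Section 4.3.3.1 also provides for reducing study medication if counts have not regenerated by day 35, which presupposes that the drug is already being taken.

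**4. What does the start day change?**

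The protocol's supply figures reproduce first. At 140 tablets per bottle and 4 tablets a day, a bottle lasts 140 / 4 = 35 days. Three bottles give 105 days, five give 175 and six give 210, all as stated in section 4.1.6. The two re-orders together give 175 + 210 = 385 days.

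| Start of the one-year clock | Year ends about day (of last course) | Tablet-days from day 8 | Re-ordered supply minus need |
|---|---|---|---|
| Day 8 | 8 + 365 = 373 | 365 | 385 − 365 = +20 |
| Day 35 (assumed end of course) | 35 + 365 = 400 | 27 + 365 = 392 | 385 − 392 = −7 |

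The protocol does not give a day for the end of a course; day 35 is assumed here as the latest control date. The comparison ignores tablets left from the three starter bottles. The clock, and the follow-up visits at 3 to 18 months after the end of maintenance, move by at most 27 days under this assumption.

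**5. Does the confirmatory analysis change?**

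No. EFS runs from day 1 of study treatment (section 7.2.1) and the stratified log-rank test is by intention to treat (section 7.2). The 191 events depend on the assumed medians of 9 and 13.5 months, not on maintenance entry.

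**The case against.** The strongest reply is that day 8 is not a decision point. The same tablets already run from that day, and 4.1.6, 4.3.4.1 and 4.3.4.2 all name it. This stands as far as exposure around the start is concerned. A reader might infer that a site waiting for a documented CR would withhold drug for about three to four weeks. The documents do not support that: dosing continues under Tables 12 and 13 whatever the phase is called. Nor is day 28 a remission-control date; it is the earliest start of a further consolidation course.

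A second reply is that CR, once reached, ends with relapse and not with cytopenia after chemotherapy. The Arm V sentence would then mean only that the patient is still in remission. Footnote b fits this view, because it asks for no repeat marrow from patients in CR. It is a reasonable guess at the intent. But the text says after consolidation and uses a defined term, and the guess settles neither the CRi patients nor the conflict with 4.3.4 and 4.3.4.1.

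Third, the arm labels are descriptive only (section 4.3.1), so the CR wording may simply be misplaced. That may be so, but a blinded site still needs one rule and the text does not say which.

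A reader might also count three competing entry rules. There are two explicit ones (4.3.4 and 4.3.4.2) and one paragraph that states no remission condition (4.3.4.1); section 4.3.3.1 governs entry to consolidation.

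**Conclusion.** The contradiction is in the current text and should be resolved. Two explicit entry rules disagree, the stricter one is written for one arm of a double-blind trial and omits CRi, and the status it asks for is not available on the stated start day. The Table 14 header adds a second start point.

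The start-day conflict is minor: at most 27 days on the one-year clock and the later visits, if the course is taken to end on day 35. The entry conflict is larger for the patients affected: up to one year of study drug, and adherent or non-adherent status in the per-protocol analysis. How many patients that is cannot be computed, because the protocol gives no expected number not in CR, or in CRi, after three courses.

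A reader might infer that selecting on count recovery biases the primary comparison. The documents do not support this: no described analysis conditions on entering maintenance, and the confirmatory test starts at day 1 by intention to treat. No sample-size or error-rate figure changes.

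**What to change.** Reconcile sections 4.1.6, 4.3.3.1 (with Tables 12 and 13), 4.3.4, 4.3.4.1, 4.3.4.2 and the Table 14 header into one entry rule and one start day that apply identically to both arms. The rule should rest on information the schedule provides by that day, and should say explicitly whether patients in CRi, or otherwise not in CR, continue study drug. State which day starts the one-year period, so that the end of maintenance and the follow-up visits are counted from the same point at every site, and make the per-protocol adherence criterion refer to that rule. Which rule and which day are the sponsor's clinical decision.

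The cost is a short amendment to section 4.3.4 with matching edits to the table header and cross-references. If the chosen start is later than day 8 while dosing still begins on day 8, the re-order quantities in section 4.1.6 need a check. No change to the sample size or the primary analysis is needed.

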#### **4.3.5 Concomitant medications/ therapy**

All appropriate palliative and supportive care for disease-related symptoms will be provided to all patients. This includes anti-emetics and other symptomatic treatments, which should be used as needed and may be given prophylactically in subsequent cycles.

Patients may receive anti-microbial prophylaxis in the presence of myelosuppression at the investigator's discretion.

G-CSF will be given at a dose or doses in accordance with the institution's standard practice regarding the use of growth factors. It is also to the discretion of the participating centers, which type of G-CSF preparation they choose to treat their patients. Available preparations are filgrastim (Neupogen®), lenograstim (Granocyte®) and the pegylated form of pegfilgrastim (Neulasta®)

## 5 STUDY PROCEDURES

### 5.1 Study evaluations

Most procedures for patient evaluation listed below are considered by the investigators to be necessary according to the standard of good clinical practice for the diagnosis and treatment monitoring of AML patients.

#### 5.1.1 Evaluations before treatment

(for full details about time points of evaluations please refer to the “schedule of evaluations”)

- Complete blood count (CBC) with differential and platelets
- Serum chemistries: electrolytes, creatinine, urea, uric acid, bilirubin, AP, AST, ALT, LDH, amylase, lipase, phosphate
- Coagulation: PTT, quick, INR, fibrinogen, ATIII
- Blood type
- Full history and clinical examination
- Serum pregnancy test for women of child bearing potential
- Vital signs, incl. blood pressure measurement
- Body height and body weight
- Performance status (ECOG)
- Electrocardiogram
- Echocardiography
- Chest X-ray
- Sonography of the abdomen
- Bone marrow aspirate and biopsy, peripheral blood cell, serum and plasma:
  - Cytomorphological examination incl. cytochemistry
  - Immunophenotyping
  - Cytogenetics
  - Molecular genetic analyses for the presence of Flt3-ITD and Flt3 point mutations, genomic ratio of Flt3-ITD vs. Flt3-WT, for NPM1 mutations, for the presence of Bcr-Abl, PML-RARalpha, AML1-ETO, inv(16), CEBP $\alpha$ , WT-1 and CBF $\beta$ -MYH11.
  - Asservation of vital bone marrow cells (Ficoll-treated bone marrow), RNA, DNA and protein lysates, serum and plasma in a central tissue repository.
  - Determination of mutations in other kinases than FLT3 (e.g. Kit, JAK2, RAF) and transcription factors (e.g. CEBP $\alpha$ , WT1)
  - Determination of methylation status of genes like p15 or p16
  - Determination of SNP's in metabolizing enzymes like e.g. of the CYP family\*

\*These analyses will be performed for exploratory research purposes and are optional.

## **Evaluations during treatment**

(for full details about timepoints of evaluations please refer to the “schedule of evaluations”)

- Bone marrow aspirate (and biopsy)
- Asservation of vital bone marrow cells (Ficoll-treated bone marrow), bone marrow RNA, DNA and protein lysates, serum and plasma in a central tissue repository
- Control of CBC (with differential and platelets), coagulation and serum chemistries (including amylase, lipase and phosphate)
- Performance status
- Physical examination
- Body weight
- Diagnostic procedures i.e. in case of severe infections will follow standard procedures and should include diagnostic measures such as chest x-ray, ultrasound, urinalysis
- Evaluations performed before the first course of induction therapy will be repeated prior to each following course if necessary in the investigator’s opinion
- ECG and echocardiography as often as necessary in the investigator’s opinion
- Daily measurement of blood pressure during the first three weeks of Sorafenib/ Placebo treatment and weekly for the following three weeks Sorafenib/ Placebo treatment

### **5.1.2 Evaluations during and/ or at the end of maintenance therapy**

(for full details about timepoints of evaluations please refer to the “schedule of evaluations”)

Performance status

Physical examination

Vital signs

- CBC (with differential and platelets), coagulation and serum chemistries (including amylase, lipase and phosphate)
- Bone marrow aspirate (and biopsy)
- Asservation of vital bone marrow cells (Ficoll-treated bone marrow), bone marrow RNA, DNA and protein lysates, serum and plasma in a central tissue repository

### **5.1.3 Evaluations during follow up (standard routine parameters)**

- Bone marrow aspirate in case of suspected relapse
- CBC with differential every 3 months
- Performance status every 3 months

### **5.1.4 Evaluations in case of relapse**

CBC with differential and platelets

- Bone marrow aspirate
- Asservation of vital bone marrow cells (Ficoll-treated bone marrow), bone marrow RNA, DNA and protein lysates, serum and plasma in a central tissue repository

## 5.2 Schedule of evaluations

	Within 10 days prior to the first course of induction therapy	Between day 1 and day 22 of first course of induction chemotherapy	Early response evaluation (d 16)	Before the second course of induction therapy	From day 1 of second course of induction chemotherapy until start of consolidation therapy	Remission control – latest 35 days after the beginning of second induction	Before each course of consolidation therapy	From the beginning of first course of consolidation until the end of third course of consolidation = beginning of maintenance therapy	Postremission control latest day 35 after begin of each course of consolidation therapy
Informed consent	X								
Medical history	X								
Performance status and physical examination	X			X			X		
Vital Signs (blood pressure and pulse) a	X	Daily measurement of blood pressure		X	weekly		X	weekly	
Body weight and height	X			X			X		
CBC (with differential and platelets) a	X	3 times / week		X	weekly	X	X	weekly	X
Chemistry and coagulation a	X	3 times / week		X	weekly		X	weekly	

	Within 10 days prior to the first course of induction therapy	Between day 1 and day 22 of first course of induction chemotherapy	Early response evaluation (d 16)	Before the second course of induction therapy	From day 1 of second course of induction chemotherapy until start of consolidation therapy	Remission control – latest 35 days after the beginning of second induction	Before each course of consolidation therapy	From the beginning of first course of consolidation until the end of third course of consolidation = beginning of maintenance therapy	Postremission control latest day 35 after begin of each course of consolidation therapy
ECG and echocardiography a	X			X			X		
Pregnancy test e	X								
Bone marrow aspirate	X		X			X			X b
Bone marrow biopsy	X								
Bone marrow and blood samples for exploratory research	X		X			X			X b

Table 14: Schedule of evaluation I (prior to and during induction/ consolidation therapy)

	Start of maintenance therapy	During maintenance therapy	End of maintenance therapy	Follow-up 3, 6, 9, 12, 15 and 18 months after end of maintenance therapy	Relapse (during study treatment or follow-up)
Performance status and physical examination	X	monthly	X	X	
Vital Signs (blood pressure and pulse) a	X	monthly	X		
CBC (with differential and platelets) a	X	monthly	X	X	X
Chemistry and coagulation a	X	monthly	X		
ECG and echocardiography a	X				
Bone marrow aspirate		X c	X	X d	X
Bone marrow and blood samples for exploratory research		X c	X	X d	X

Table 15: Schedule of evaluation II maintenance therapy + follow-up)

- a These evaluations should be repeated as often as necessary in the opinion of the treating physician  
b For patients who are in a morphologic leukemia-free state (until relapse or CR) or suspected relapse  
c One month after beginning of maintenance therapy and then every 3 months or at suspected relapse  
d For patients with suspected relapse  
e Pregnancy tests are to be performed for woman with child-bearing potential only.

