### 3.4 Removal of patients from study

A patient who withdraws is one who discontinues participation in a clinical study for any reason.

Patients may be withdrawn from the trial for the following reasons:

- At their own request or at the request of their legally acceptable representative
- If, in the investigator's opinion, continuation in the study would be detrimental to the patient's well-being
- At the specific request of the sponsor

Patients must be withdrawn also for the following reasons:

- In case of unacceptable toxicity or progressive disease
- In case of substantial non-compliance with the requirements of the study
- Positive beta-HCG test consistent with pregnancy. Pregnancy will be reported along the same time lines as a serious adverse event

- Use of illicit drugs or other substances that may, in the opinion of the investigator, have a reasonable chance of contributing to toxicity or otherwise skewing results
- Development of an intercurrent illness or situation which would, in the judgment of the investigator, affect assessments of clinical status and study endpoints to a significant degree
- Development of a second cancer that requires treatment
- Patient is lost to follow-up
- Interruption in study drug administration for a period longer than 28 consecutive days
- Patient death

Relevant visit data will be entered into the CRF, and any unused study medication will be accounted for and returned for all subjects entered into the trial even if for a brief period of time. Subjects who discontinue study treatment will have relevant information completed and recorded in the CRF and medical record. All subjects who discontinue because of adverse events or clinical laboratory abnormalities should be followed up until they recover or stabilize and the subsequent outcome recorded.

In case of premature withdrawal of any cause, all data documented up to the date of withdrawal will be entered into the study analysis.

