#### **6.3.1.2 Special Warnings and Precautions for Use**

Nexavar® (Sorafenib) is approved for treatment of patients with hepatocellular carcinoma and advanced renal cell cancer. Because this is a novel agent, current knowledge of the adverse events associated with this compound is limited. As with any new chemical entity, there is always potential for unexpected adverse events.

**Pregnancy:** Women should avoid becoming pregnant while on therapy.

Women of childbearing potential must be apprised of the potential hazard to the fetus, which includes severe malformation (teratogenicity), failure to thrive and fetal death (embryotoxicity).

Sorafenib should not be used during pregnancy. Prescribers may only consider it to be used, if the potential benefits justify the potential risks to the fetus.

Based on the proposed mechanism of multikinase inhibition and multiple adverse effects seen in animals at exposure levels significantly below the clinical dose, Sorafenib should be assumed to cause fetal harm when administered to a pregnant woman.

Breastfeeding should be discontinued during Sorafenib therapy.

**Dermatological Toxicities:** Hand-foot skin reaction (palmar-plantar erythrodysesthesia) and rash represent the most common adverse drug reactions with Sorafenib. Rash and hand-foot skin reaction are usually CTC (National Cancer Institute Common Toxicity Criteria) Grade 1 and 2 and generally appear during the first six weeks of treatment with Sorafenib. Management of dermatologic toxicities may include topical therapies for symptomatic relief, temporary treatment interruption and/or dose modification of Sorafenib, or in severe or persistent cases, permanent discontinuation of Sorafenib.

**Hypertension:** An increased incidence of hypertension was observed in Sorafenib-treated patients. Hypertension was usually mild to moderate, occurred early in the course of treatment, and was amenable to management with standard antihypertensive therapy. Blood pressure should be monitored regularly and treated, if required, in accordance with standard medical practice. In cases of severe or persistent hypertension, or hypertensive crisis despite adequate antihypertensive therapy, permanent discontinuation of Sorafenib should be considered.

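### Only one pregnancy test is required, before induction, and none is provided for in the year of continuous maintenance, although the protocol assumes Sorafenib harms the fetus

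*Protocol*

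**What the plan says.** - **Before treatment.** Section 5.1.1 lists a serum pregnancy test for women of childbearing potential. Table 14 in section 5.2 has a single mark for it, in the column headed "Within 10 days prior to the first course of induction therapy". Section 3.1.2 requires a negative result within 7 days before treatment starts.
- **Footnote.** The test carries only footnote e: "Pregnancy tests are to be performed for woman with child-bearing potential only". Footnote a, which lets an evaluation be repeated as often as the physician thinks necessary, is attached to vital signs, blood count, chemistry and coagulation, and ECG and echocardiography. It is not attached to the pregnancy test.
- **Later courses.** Under the heading on evaluations during treatment (section 5.1): "Evaluations performed before the first course of induction therapy will be repeated prior to each following course if necessary", with the need judged by the investigator.
- **Maintenance.** Section 5.1.2 lists performance status, physical examination, vital signs, "CBC (with differential and platelets), coagulation and serum chemistries (including amylase, lipase and phosphate"), and bone marrow and stored samples. A pregnancy test is not among them, and Table 15 has no row for one.
- **Exposure.** Section 4.3.4.2: "Maintenance therapy will start on day 8 of the last consolidation cycle", and "Maintenance therapy will be administered continuously until one year after start of maintenance therapy". Section 4.3.4.1 gives the placebo arm the same timing.
- **Risk and consequence.** Section 6.3.1.2: "Sorafenib should be assumed to cause fetal harm when administered to a pregnant woman". Section 3.4 lists "Positive beta-HCG test consistent with pregnancy" among the reasons for which a patient must be withdrawn, and has pregnancy reported as quickly as a serious adverse event. Section 6.3.1.4 advises women to use two contraceptive methods.

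**The concern.** The protocol treats the drug as a presumed teratogen and has a rule for a pregnancy on study, but its visit schedule contains no step that would find one. Maintenance is the longest uninterrupted exposure in the trial, and it is also the only treatment phase in which the text offers neither a scheduled nor a discretionary test.

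A site that follows the tables exactly could see a woman every month, draw blood each time, and continue study drug through the early weeks of a pregnancy until it became clinically apparent. At stake is avoidable fetal exposure.

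**Working it through.** There is no sample-size or error-rate figure to reproduce. The check is a count of tests and intervals from the schedule.

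**Required tests, by phase**

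| Phase | Required | Discretionary provision |
|---|---|---|
| Before induction I (Table 14; 3.1.2) | 1 | – |
| Before induction II | 0 | yes, investigator's opinion |
| Before each of 3 consolidation courses | 0 | yes, investigator's opinion |
| Start, course and end of maintenance (Table 15; 5.1.2) | 0 | none written |

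Required tests after baseline: 0, against a treatment duration of approximately 18 months (section 5.3).

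**Longest stretch without any provision.** The last permitted discretionary repeat is before day 1 of consolidation course 3. Maintenance starts on day 8 of that course and lasts one year:

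(8 − 1) + 365 = 7 + 365 = 372 days.

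This is a minimum. It assumes the investigator uses the discretion and tests immediately before the course.

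**Timing of the baseline test.** Study drug starts on day 10 of induction (section 4.3.2), 9 days after day 1. The one required test can therefore precede the first dose by up to 7 + 9 = 16 days under section 3.1.2, or 10 + 9 = 19 days under the Table 14 column window.

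**Tests added by the proposed schedule**

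- Before courses: induction II (1) + consolidation (3) = 4.
- Maintenance: start (1) + months 1 to 11 (11) + end at month 12 (1) = 13.
- Total: 4 + 13 = 17.

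The longest gap between tests in maintenance becomes one month, about 31 days.

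**Whether extra visits are needed.** Chemistry and coagulation are already scheduled before induction II and before each consolidation course (Table 14: 4 of 4 time points). In maintenance they are scheduled at the start, monthly and at the end (Table 15: 13 of 13). None of the 17 tests needs a new visit.

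**The case against.** The strongest reply is that protection already exists. Pregnant women are excluded by test, and women are to be told of the hazard and advised to use two contraceptive methods. Nothing forbids a test on clinical suspicion at a monthly visit, and the withdrawal rule in section 3.4 works however a positive result arises. On that reading there is no contradiction, only missing backup detection.

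Much of this is fair. Section 3.4 is not contradicted, and contraception is the main safeguard. But contraception cannot show that it has failed, and a test prompted by suspicion comes after exposure has begun.

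Further points have some force:

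- **The size is a count of tests and days, not of expected pregnancies.** The protocol gives no number of women of childbearing potential, so the risk cannot be quantified. Only women on Sorafenib, about half under 1:1 allocation, are exposed to its specific harm. Because the trial is blinded, the test must still apply to both arms.
- **The long intervals apply only to women who complete treatment.** Patients who go to transplantation or fail induction stop study drug earlier.
- **Monthly is not the only defensible interval.** Marrow in maintenance is examined after one month and then every three months. A three-monthly test would leave gaps of up to about 92 days rather than 31. Monthly is proposed because the visits and blood draws are already monthly.
- **The added schedule leaves the interval between baseline test and first dose unchanged.** That is true, but at up to 16 days under the eligibility rule it is shorter than the monthly gap proposed for maintenance.
- **HCG is not in the listed chemistry panel.** It is an extra assay even where blood is already drawn.
- **Other guidance cannot be seen.** The consent pages are not available and the protocol refers to the prescribing information, so sites may have further instructions. That would not alter the protocol's own tables.

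**Conclusion.** The concern holds. The protocol requires one pregnancy test, before induction. It leaves repeats before later courses to opinion and provides for none in maintenance. For a woman who completes treatment this means 0 required tests after baseline over about 18 months, and at least 372 days without even a discretionary provision.

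These figures rest on the written schedule and assume three consolidation courses and a full year of maintenance. The number of women affected and the chance of pregnancy are not given and are not estimated here. The change should be made for participant safety; it does not bear on the primary analysis. The maintenance gap is the core of the point, and the optional pre-course tests are the lesser part.

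**What to change.** For women of childbearing potential who remain on study treatment:

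1. In Table 14, mark a pregnancy test before induction II and before each consolidation course.
2. In Table 15, add a pregnancy-test row: start of maintenance, each monthly visit, and end of maintenance. Add the same item to section 5.1.2.
3. Keep footnote e. State that a positive result is confirmed before the section 3.4 withdrawal rule is applied.
4. As an editorial alignment only, label the baseline cell in Table 14 with the 7-day limit of section 3.1.2, counted back from day 1 of induction.

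**Cost.** At most 17 added assays per woman who completes treatment, on blood drawn at existing visits. The assay price is not in the protocol; it is assumed to be small. No visit is added, and eligibility, blinding, sample size and analysis are unchanged. The drawback is an occasional false positive that needs a confirmatory test.
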